Integrate Study

Statistical Analysis Plan

Does cannabidiol attenuate the acute effects of $\Delta 9$ -tetrahydrocannabinol intoxication in individuals diagnosed with schizophrenia? A double-blind, randomised, placebo-controlled experimental study

Version: 1.0
Date: 28/07/2023

IRAS: 278595
ClinicalTrials.gov: NCT04605393

Authors: [name], [name], [name], [name], [name], [name], [name]

Study Design

Integrate is a double-blind, randomised, placebo-controlled, crossover, experimental study assessing whether pre-treatment with oral cannabidiol (CBD) can attenuate the negative effects of acute delta-9-tetrahydrocannabinol (THC) intoxication in individuals with schizophrenia or schizoaffective disorder who use cannabis.

Population

The study will recruit 30 participants with a diagnosis of schizophrenia or schizoaffective disorder, who smoke cannabis regularly, are currently receiving treatment with antipsychotic medication, and are clinically stable (no inpatient or intensive community care for at least three months). Full inclusion and exclusion criteria are described in the study protocol.

Drug conditions

There are two drug conditions:

- i) CBD 1000mg oral & THC inhaled
- ii) Placebo oral & THC inhaled

Each participant will complete two experiments so that they receive each treatment once. The order of CBD/placebo is randomised and double-blind. CBD/placebo capsules are administered with food (two yoghurts).

After completing trial experiments at 10mg and 15mg, the starting dose of THC was set at 20mg (101mg of 19.8% THC ground cannabis flos).

The THC is administered three hours after CBD administration using a medical grade vaporiser device.

Dose escalation

If a participant completes two experimental visits and does not demonstrate a significant response (defined as a PANSS positive subscale score increase of 3 or more), they will be invited to complete another pair of experiments with a higher dose of THC. The dose of CBD will always be 1000mg.

[figure not shown]
Experiments 1 & 2: 20mg THC inhaled & oral CBD 1000mg/placebo

Experiments 3 & 4: 40mg THC inhaled & oral CBD 1000mg/placebo

Experiments 5 & 6: 60mg THC inhaled & oral CBD 1000mg/placebo

With each pair of experiments participants will be re-randomised to treatment with CBD/placebo.

Flowchart

Study objective

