Analysis of primary and secondary outcome measures

Continuous outcomes will be reported as means with standard deviation. Categorical outcomes will be reported as frequencies.

We will use linear mixed models to assess the effect of CBD on all continuous outcomes. Treatment allocation (CBD/placebo) and visit number will be included as categorical fixed effects, with participant as a random effect to account for the dependency between repeated measures. Estimated marginal means will be calculated and compared in a pairwise test. If residuals do not fit a normal distribution, values will be transformed to fit a normal distribution.

P values below 0.05 will be considered significant. All tests will be two-tailed.

Analysis of VAS

Two comparisons will be made for each outcome: i) effect at 10mins post-THC; and ii) total effect over time (AUC from pre-THC timepoint to End of Study timepoint). For calculation of AUC, the pre-THC timepoint will be set at -20mins and the end of study visit will be set at +135mins post-THC. We will use a linear mixed-model for this comparison.

Analysis of STAI-S

The STAI-state scale was administered at three timepoints during each experiment: pre-CBD/placebo, pre-THC and post-THC. Here, the outcome of primary interest is the difference between baseline anxiety and post-THC anxiety. An additional and separate analysis will be completed to assess whether CBD can reduce anxiety prior to THC intoxication. We will use a linear mixed-model for this comparison.

Pharmacokinetic analyses

Pharmacokinetic parameters will be summarized descriptively. We will report the geometric mean of the AUC_t and C_{max} . THC's AUC will be calculated from 0mins – 90mins.

To compare the C_{max} and AUC_t of THC and its metabolites across treatment arms, we will use a paired sample t-test or a Wilcoxon rank sum test, depending on the distribution of the data.

DOES CANNABIDIOL ATTENUATE THE ACUTE EFFECTS OF Δ9-TETRAHYDROCANNABINOL INTOXICATION IN INDIVIDUALS DIAGNOSED WITH SCHIZOPHRENIA? A DOUBLE-BLIND, RANDOMISED, PLACEBO-CONTROLLED EXPERIMENTAL STUDY

Study Acronym: INTEGRATE

Academic Sponsor

[name], King's College London
[name]
[name], [contact]

NHS Sponsor:

[name], South London and Maudsley NHS Foundation Trust
R&D Department, [name], Institute of Psychiatry, Psychology & Neuroscience (IoPPN), [name]
[contact] , [name]

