3.5.1 Timetable

Experimental Visit Timetable	Event	Time post-completion of THC administration	Expected Time
Preparation & Baseline Psychopathological Testing	Pregnancy, Alcohol & Drug Testing Mental state review Cannula Insertion Blood sampling I Visual Analogue Scales I STAI-S I SSPS I PANSS I PSI	-3.5hrs	10am-10.30am
CBD/Placebo	Oral CBD/Placebo Administration	-3hrs	10.30am
Light lunch	Light lunch	-90min	12pm-12.30pm
Light lunch	Visual Analogue Scales II Blood sampling II		
THC Administration	Visual Analogue Scales III (pre-dosing) STAI-S II (pre-dosing) Inhalation Procedure	-30mins	1pm-1.30pm
Initial Assessments	Blood sampling III Blood sampling IV Visual Analogue Scales IV PANSS II (initial assessments) Blood sampling V	0min +5min +10min +15min	
Cognitive and Psychopathological Testing	Hopkins Verbal Learning Test (5min) Digit Span (5min) White Noise Task (7min) Advice Taking Task (8 min) Hopkins VLT - delayed recall (2min) Visual Analogue Scales V (2min) Blood sampling VI Visual Analogue Scales VI STAI-S III	+20min +45min +90min	1.50pm 2.15pm 3pm
End of day review and final outcome measures	Visual Analogue Scales VII SSPS II PANSS II (final interview and scoring) PSI	+3.5hrs	5pm
Sobriety Assessment	Sobriety Assessment		
Discharge	Discharge	4hrs	5.30pm

STAI-S: State-Trait Anxiety Inventory-State Scale
SSPS: State Social Paranoia scale
PANSS: Positive and Negative Syndrome Scale
PSI: Psychotomimetic States Inventory

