3.6.5 Other outcome measures

Psychotomimetic States Inventory (PSI).

A 48-item questionnaire that measures psychotic-like experiences. The PSI was developed for use in drug studies, particularly cannabis and ketamine studies (Mason et al., 2008). Items are rated on a 4-point scale (from 0 = never to 3 = strongly). The PSI has subscales of delusionary thinking, perceptual disorders, cognitive disorganisation

State-Trait Anxiety Inventory-State (STAI-S)

This is a 20-item scale which measures current state of anxiety (Spielberger 1983). Each item is scored from 1 (not at all) to 4 (very much).

Visual analogue scales (VAS)

These will be used to measure contemporary subjective experiences. The scales ranges will range from 0 to 10. The following scales will be used:

- Feel drug effect
- Like drug effect
- Want more drug
- Thinking clearly
- Tired
- Excited
- Want to talk
- Anxious
- Relaxed
- Happy
- Irritable
- Suspicious
- Hearing voices
- Dry mouth
- Hungry

- Vulnerable
- Threatened

As the study progresses, additional visual analogue scales may be added if it becomes apparent that relevant symptoms are not accounted for.

Preference for overall drug experience

At the end of the second experimental visit, participants will be asked which of the two drug experiences they preferred. They will be asked to describe the reasons for this decision.

Opinion on CBD as a potential harm reduction treatment

Participants will be asked to discuss their thoughts regarding CBD as a novel treatment. Before answering questions, they will be asked to assume that CBD is effective at reducing psychosis symptoms and the risk of relapse. They will then answer a series of specific and open-box questions regarding:

- Indication for treatment (psychosis treatment vs. cannabis harm-reduction vs. other indications)
- Polypharmacy with antipsychotic medication (ie. an adjunct to antipsychotic medication vs. to enable antipsychotic dose to be reduced vs. CBD monotherapy)
- Concerns regarding adverse effects
- Formulation (tablets, capsules, oil, other)
- Natural vs. synthetically derived CBD

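### The VAS models make no use of the reading taken before CBD/placebo at each visit; adding it as a covariate is a cheap gain in precision

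*Combined protocol and SAP*

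**What the plan says.** SAP, Analysis of VAS: each scale gets a comparison at 10 minutes after THC and a second one on the "total effect over time (AUC from pre-THC timepoint to End of Study timepoint". The limits are fixed: "For calculation of AUC, the pre-THC timepoint will be set at -20mins and the end of study visit will be set at +135mins post-THC". Neither definition subtracts or adjusts for a starting level.

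SAP, Analysis of primary and secondary outcome measures, gives the model for all continuous outcomes: "Treatment allocation (CBD/placebo) and visit number will be included as categorical fixed effects, with participant as a random effect". No baseline covariate is named.

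Protocol section 3.5.1 lists "Visual Analogue Scales I" in the preparation block, before the CBD/placebo capsule. It lists "Visual Analogue Scales III (pre-dosing") just before inhalation, some two and a half hours after the capsule. Section 3.6.5 names 17 scales and says of them "The scales ranges will range from 0 to 10".

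Elsewhere the SAP does use the pre-capsule timepoint: PANSS positive and STAI-S are both scored as the post-THC value minus the value before CBD/placebo.

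**The concern.** Several of the scales (Hearing voices, Suspicious, Anxious, Tired, Happy) need not be zero before any study drug in people with schizophrenia. Nor need they be the same on two days at least a week apart. The participant random effect deals with a level that a person carries to both visits. It does not deal with arriving more tired or more anxious at one visit than at the other. That difference passes into the CBD-placebo difference as error.

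The plan makes 17 × 2 = 34 VAS comparisons. Leaving out Feel drug effect, Like drug effect and Want more drug, for which a reading before any drug should say little, 14 × 2 = 28 comparisons could gain from a reading that is already collected. What is at stake is precision on secondary outcomes, not validity.

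**Working it through.** **1. The plan's own figure.** Protocol section 5.1 gives n=30 pairs, two-sided alpha 0.05, d=0.53 and 80% power. Noncentral t with 29 df and noncentrality 0.53 × √30 = 2.903 gives 80.1%, so the figure reproduces. With visit number in the model (28 df) it is 80.0%, the reference below. No power figure is given for the VAS, so d=0.53 is borrowed as an illustration.

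**2. What cancels and what does not.** Take the SAP limits of -20 and +135 minutes, with readings between them at +10, +45 and +90 (my reading of a timetable that is broken in the text). The trapezoid weights are 15, 32.5, 40, 45 and 22.5 minutes; they sum to 155 and their squares sum to 5412.5. Assume independent noise of SD 1 per reading.
- No difference between people: SD of the AUC = √5412.5 = 73.6.
- Personal levels with SD 3: SD of the AUC = √(5412.5 + 9 × 155²) = 470.8.
- SD of the paired CBD-placebo difference in both cases: √(2 × 5412.5) = 104.0.

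Stable levels therefore drop out. A one-point shift of a whole visit does not: it moves that visit's AUC by 155, wherever the intermediate readings fall.

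**3. Gain from VAS I as a covariate.** Adjustment multiplies the error variance of the paired difference by 1 - rho². Noncentrality becomes 2.903 / √(1 - rho²) × √(27/28), with 27 df. The last factor is an approximate allowance for estimating one within-participant slope.

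| assumed rho | 1 - rho² | noncentrality | power |
|---|---|---|---|
| 0 | 1.00 | 2.851 | 78.5% |
| 0.2 | 0.96 | 2.909 | 80.1% |
| 0.3 | 0.91 | 2.988 | 82.1% |
| 0.5 | 0.75 | 3.292 | 88.7% |
| 0.7 | 0.51 | 3.992 | 97.0% |

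Unadjusted power is 80.0%, so break-even is near rho=0.2 and the worst loss is about 1.5 points.

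**4. Why a covariate and not a change score.** Let b be the assumed share of within-participant variance that is a common visit level, the rest being independent noise. The variance of the paired AUC difference is then:
- as planned: 2(155²b + 5412.5(1 - b));
- change from VAS I: 2(5412.5 + 155²)(1 - b);
- VAS I as covariate: the planned variance minus (2 × 155b)²/2.

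At b=0.2 these are 18,270, 47,100 and 16,348. At b=0.5 they are 29,437.5, 29,437.5 and 17,425. With the planned analysis set at 80% power (29 df, no slope allowance), the change score gives 42% and 80%, and the covariate 84% and 95%.

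**5. Why not the pre-THC reading.** If CBD lowers a scale by one point from before THC onward, the AUC as planned shows -155. With the pre-THC reading subtracted throughout it shows -155 + 155 = 0.

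**The case against.** The strongest reply is that nothing here is wrong. By design, "Each participant will complete two experiments so that they receive each treatment once", and the protocol synopsis defines the secondary endpoints as differences between the test conditions. Effect at 10 minutes and total effect can then be read as the CBD-placebo contrast at one time and over time, for which levels compared within a person are legitimate. That stands: the planned contrast is valid. It also stands that rho is unknown, that adjustment costs a little power below about 0.2, and that the illustration uses alpha 0.05 although the SAP applies Benjamini-Hochberg across the VAS. What is left is the chance of a useful gain against a small, bounded loss.

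Two stronger readings are tempting.

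A reader might infer that the AUC is defective because a non-responder can outscore a responder. A flat record of 4 scores 4 × 155 = 620, while a response of 0, 4, 3, 1, 0 scores 4 × 32.5 + 3 × 40 + 1 × 45 = 295. But this compares two people, and no planned VAS analysis ranks people; response is defined on PANSS positive. Counting the pre-THC reading is not the cause either. Started at +10 minutes (weights 17.5, 40, 45, 22.5), the scores are 4 × 125 = 500 and 4 × 17.5 + 3 × 40 + 1 × 45 = 235.

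A reader might also infer that the pre-THC reading should be the reference. It is taken after CBD/placebo and may carry CBD effect. The SAP itself plans a separate test of CBD on STAI-S before THC.

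**Conclusion.** A cheap improvement, not an error. The documents do not support a claim of bias, since order is randomised and stable levels cancel, nor a claim that the AUC window is wrong. They do show a starting value collected at each visit, used for PANSS positive and STAI-S, and left out of both VAS analyses without a stated reason.

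The size is a range: roughly 2, 9 and 17 points of power gained at assumed rho of 0.3, 0.5 and 0.7, nothing near 0.2, and about 1.5 points lost at 0. This rests on 30 complete pairs, a borrowed d of 0.53, unadjusted alpha and an unknown rho that will differ by scale. That these scales vary between visits is plausible but also an assumption. The power table does not depend on the AUC reading times.

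**What to change.** In the SAP, Analysis of VAS, for every scale except Feel drug effect, Like drug effect and Want more drug:
- add that visit's VAS I score and the participant's mean VAS I score as covariates in both the 10-minute and the AUC model; the mean keeps the slope on the visit score within participant;
- report the adjusted CBD-placebo difference, and say that this contrast is what is meant by effect;
- do not subtract the pre-THC reading (VAS III).

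The AUC window can stay as planned. Separately, the SAP's -20 and +135 minutes should be reconciled with the timetable in protocol section 3.5.1, which appears to put VAS III at -30 minutes and the last VAS at +3.5 hours.

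Cost: SAP wording and one within-participant slope per model. No new data or visits.

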5.2 Analysis

Study data will be analysed following the completion of data collection and database lock. For the primary analysis linear mixed models will be used, with fixed effects of experimental condition and random intercept for repeated measures within participants. Differences in the frequency of categorical data will be analysed using Pearson's Chi-square test or multilevel logistic regression as appropriate. Relationships between cognitive, intermediate and psychosis data will be analysed using

Pearson's or Spearman's rank correlation coefficient. If data do not fit a normal distribution they will be analysed after appropriate transformation. We will present both effect sizes and tests addressing study hypotheses with statistical significance set at $p < 0.05$. All tests will be two-tailed.

6 Participant reimbursement

Participants will be reimbursed for their time at a rate equivalent to the London Living Wage (£10.55/hour). The baseline assessment is expected to take 4 hours and each experimental visit is expected to take up to 8 hours, a total of 20 hours. The total payment for completing the study (ie. two experiments with THC 20mg) will be £200. The participant will be paid £30 for the baseline, £70 for experimental visit 1 and £100 for experimental visit 2. Further reimbursement will be provided if a participant attends experimental visits 3 (£70), 4 (£100), 5 (£70) and 6 (£100). The total payment for attending all visits will be £540. Participants who do not complete all study visits will be reimbursed for the number of study visits they have attended. Participant will be paid either in cash or via bank transfer as per their preference. For bank transfers, bank details will be taken from the participant at the end of the study and payment will be processed 2-4 weeks after the final study visit.

7. Trial Steering Committee

The trial steering committee will supervise the trial on behalf of the sponsor, ensuring that the study is conducted under good clinical practice (GCP). In addition the trial steering committee will monitor progress of the trial, monitor adherence to the protocol and monitor participant safety. The trial steering committee will include [name], [name], [name] and [name].

8. Access to Source Data and Documents

The researchers will permit study-related monitoring, audits, REC review, and regulatory inspections by providing the Sponsor(s), Regulators and REC direct access to source data and other documents.

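### The SAP sets the end-of-study VAS at +135 min for the AUC, the protocol timetable schedules it at +210 min, and neither document explains the gap

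*Combined protocol and SAP*

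**What the plan says.** The SAP (Analysis of VAS) makes two comparisons for each scale: the "effect at 10mins post-THC" and the "total effect over time (AUC from pre-THC timepoint to End of Study timepoint". It then fixes the two ends of the window: "the pre-THC timepoint will be set at -20mins and the end of study visit will be set at +135mins post-THC". It gives no source for either nominal time and does not name the rule for calculating the area.

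The protocol timetable (section 3.5.1) counts time under the column "Time post-completion of THC administration". Three places matter here:

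- The pre-THC scale is in the block "Visual Analogue Scales III (pre-dosing) STAI-S II (pre-dosing) Inhalation Procedure", labelled -30 min, 1pm to 1.30pm.
- The testing block carries the offsets "20min +45min +90min".
- The last scale is in the end-of-day block, "Visual Analogue Scales VII SSPS II PANSS II (final interview and scoring) PSI", at +3.5 hours, 5pm.

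No VAS is listed between +90 min and that last block.

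**The concern.** VAS VII is the only assessment that can be the SAP's end-of-study point, and the two documents time it 75 minutes apart. If the scale was completed as scheduled but entered at +135, the last interval of the AUC is 45 minutes instead of 120. The total effect over time would then describe a shorter window than the one observed, with less weight on the last two readings. This would apply to all 17 scales listed in the protocol, for one of the only two comparisons that the SAP makes on each. A reader with both documents cannot tell which window the result describes.

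**Working it through.** **1. Can +135 be reproduced from the timetable?** The clock times and offsets agree on time zero at 1.30pm: 1.50pm is +20, 2.15pm is +45, 3pm is +90, 5pm is +210 and 5.30pm is +240 (4 hours). So +135 would be 3.45pm, when nothing is scheduled. The gap is 210 - 135 = 75 min. Counting from the start of the inhalation block (1pm) would not close it, because 5pm would then be +240. The figure does not reproduce.

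**2. Trapezoid weights.** Inputs: VAS III at -20 (SAP), VAS IV at +10 (SAP), VAS V at +45 and VAS VI at +90 (section 3.5.1). The +90 reading comes from a table row that has run together. It is supported by blood sample VI, listed just before VAS VI, and by the 90-minute sample in section 3.6.2. The linear trapezoid is an assumption. Each point's weight is half the sum of its adjacent intervals.

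| VAS VII at | III | IV | V | VI | VII | Total (min) | Share of VII |
|---|---|---|---|---|---|---|---|
| +135 | 15 | 32.5 | 40 | 45 | 22.5 | 155 | 22.5/155 = 14.5% |
| +210 | 15 | 32.5 | 40 | 82.5 | 60 | 230 | 60/230 = 26.1% |

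The weights differ only at VAS VI and VII, by 37.5 each. The area left out per visit is therefore 37.5 x (VAS VI + VAS VII) point-min.

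**3. Sensitivity of the shares (+135 against +210).**

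- Start at -30: 22.5/165 = 13.6% against 60/240 = 25.0%.
- VAS VI at +75: 30/155 = 19.4% against 67.5/230 = 29.3%.
- VAS VI at +105: 15/155 = 9.7% against 52.5/230 = 22.8%.
- VAS VII in between: 37.5/185 = 20.3% at +165 and 45/200 = 22.5% at +180.
- The time of VAS V does not affect the share.

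**4. Effect on the result.** The CBD-placebo difference patterns are assumptions, given at VAS IV, V, VI, VII, with no difference at VAS III. The raw AUC difference is the weighted sum w'd. The standardised effect is w'd / sqrt(w'Cw), with equal variances and an equal correlation rho from 0 to 0.7 between time points, so that w'Cw is proportional to (1 - rho) x sum(w^2) + rho x (sum w)^2.

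| Assumed difference | Raw, +135 | Raw, +210 | Raw ratio | Standardised ratio |
|---|---|---|---|---|
| Constant (1, 1, 1, 1) | 140 | 215 | 0.65 | 0.97 to 1.02 |
| Late only (0, 0, 1, 1) | 67.5 | 142.5 | 0.47 | 0.71 to 0.74 |
| Fading (1, 0.75, 0.5, 0.25) | 90.6 | 118.8 | 0.76 | 1.14 to 1.20 |
| Early only (1, 1, 0, 0) | 72.5 | 72.5 | 1.00 | 1.49 to 1.57 |

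Example, constant difference with rho = 0: sum(w^2) is 5412.5 and 13287.5. The standardised effects are 140/73.57 = 1.903 and 215/115.27 = 1.865, a ratio of 1.02.

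**The case against.** The best defence is that +135 is the informed value. The SAP (28/07/2023) is later than protocol version 5.0 (08/11/2022) and describes some conduct in the past tense. Its -20 start also departs from the timetable's -30 block, and two specific values that are not in the timetable look more like chosen nominal times than a slip. The timetable gives expected times, and section 3.6.1 lets participants take breaks. Protocol timing is also not fully consistent elsewhere. Section 3.6.2 equates 1.5 hours after CBD with 30 minutes before inhalation, whereas the timetable puts that time at 12pm, one hour before the 1pm block. An out-of-date timetable is therefore plausible. All of this stands, but it is inference: neither document says that +135 was observed or chosen.

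The length of the visit does not settle the matter. Protocol section 6 says that "each experimental visit is expected to take up to 8 hours", which fits the 10am to 5.30pm day but, as an upper limit, fits an earlier finish equally well.

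It is also fair that the raw ratio of 0.65 mostly reflects window length. Divided by the window, the same constant effect is 140/155 = 0.90 against 215/230 = 0.93 points.

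A reader might infer that the SAP value is simply wrong and that the AUC should weight VAS VII at 26.1%. The documents do not support that. The figure holds only if the timetable was followed, the rule is a linear trapezoid and VAS VI was at +90.

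**Conclusion.** The contradiction between the two documents is definite and unexplained. Its effect on the analysis is conditional. If VAS VII was taken at +210, the planned AUC covers 155 of 230 minutes, VAS VII is under-weighted, and the raw difference is too small for any pattern that persists to the last two readings in one direction. The effect on sensitivity has no fixed direction, and no section of either document predicts which pattern will hold. If VAS VII was taken near +135, the AUC is right and only the timetable needs correcting.

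A reader might also infer that the mistiming favours one arm. It does not by itself, because the same nominal times apply to both conditions within each participant. With no CBD effect at any time point, the expected weighted difference is zero under either set of weights, so type I error is unaffected. The +10 min VAS comparison, Hypotheses 1 to 4 and the primary outcomes are also untouched. The point should be settled before the VAS AUC is analysed, but it is confined to that secondary analysis.

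**What to change.** Before the VAS AUC analysis, and before unblinding if that has not yet happened:

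1. Check source records for when VAS III and VAS VII were actually completed.
2. Calculate the AUC with the recorded times. If nominal times are kept, use the typical recorded time (+210, +135 or a value between) and state its source. Apply the same approach to the start time.
3. If truncation at +135 is deliberate, say so and say how the value at +135 is obtained.
4. Name the AUC rule.
5. Reconcile the SAP and the section 3.5.1 timetable with what the records show.

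The cost is a short records check and one or two sentences in the SAP or a timetable correction. No new assessments are needed.

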To assess the extent to which, in individuals with schizophrenia, the presence of CBD attenuates the acute effects of THC on cognitive impairment and psychotic symptoms.

Primary hypotheses and outcome measures

Hypothesis 1: CBD will reduce the impairment in delayed verbal recall compared with placebo.

Outcome measure: Hopkins verbal learning task – delayed verbal recall. The total number of words correctly recalled at 20-25 minutes.

Hypothesis 2: CBD will reduce the severity of positive psychotic symptoms compared with placebo.

Outcome measure: Positive and Negative Syndrome Scale (PANSS) - Positive subscale. Change from pre-CBD/placebo to post-THC.

Secondary hypotheses and outcome measures

Hypothesis 3: CBD will reduce state anxiety compared with placebo.

Outcome measure: State-Trait Anxiety Inventory (STAI-S). Change from pre-CBD/placebo to post-THC.

Hypothesis 4: CBD will reduce the impairment in working memory compared with placebo.

Outcome measure: Forward and reverse digit span. The total number of numbers correctly repeated.

Data processing and statistical analysis

Data processing and missing data

Multiple imputation chain equations (MICE) will be used to impute missing values in psychopathological, cognitive, physiological, and pharmacokinetic outcomes using the mice package in R. We will complete sensitivity analyses to assess the effect of data imputation.

Analysis population

Primary analyses will be per-protocol (i.e. data where participants completed a pair of experiments). For participants who completed more than one pair of experiments, the data from the experiments where the highest THC dose was administered will be used. We will complete sensitivity analyses i) using the data from all participants who completed pairs of experiments with 20mg THC; and ii) intention to treat analyses.

Order effects

It will be assumed that there are no carryover effects from the previous experimental session as there was sufficient time for drug washout between session. A period effect may be present due to learning and because participants become more comfortable with the lab environment over time. We will therefore include visit number in all models to account for potential order effects.

Correction for multiple comparisons

Benjamini Hochberg correction will be conducted across outcomes locally i.e. across secondary cognitive outcomes, secondary psychopathological outcomes, visual analogue scales and physiological outcomes.

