Secondary Endpoints	
All measures will be collected at baseline and then during both test conditions. Endpoints will be the difference between the test conditions.
 
1. Cognition
o HVLT-R Immediate verbal recallo Forward and reverse digit span2. Psychotic symptoms
o Positive and Negative Syndrome Scale (PANSS)
▪ Positive subscale▪ Negative subscaleo State Social Paranoia Scale (SPSS)3. White Noise Task4. Advice Taking Task5. Psychotomimetic States Inventory (PSI)6. State-Trait Anxiety Inventory (STAI-S)7. Visual analogue scales: Feel drug effect, Like drug effect, Want more drug, Thinking clearly, Tired, Excited, Want to talk, Anxious, Relaxed, Happy, Irritable, Suspicious, Hearing voices, Dry mouth, Hungry, Vulnerable, Threatened.8. Preference for overall drug experience and opinion on CBD as a potential harm reduction treatment9. The difference in plasma levels of THC, CBD, and their metabolites10. The difference in plasma endocannabinoid levels and potential biomarkers and inflammatory markers

Sample size	
The study aims to achieve 30 complete datasets. Accounting for an estimated 25% drop-out rate it is expected to recruit 40 participants.

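### The SAP's non-parametric fallback for the paired pharmacokinetic comparison is an unpaired test (Wilcoxon rank-sum), which loses power for modest changes in THC exposure

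*Combined protocol and SAP*

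**What the plan says.** The design is a crossover. Under Drug conditions the SAP states: "Each participant will complete two experiments so that they receive each treatment once". Under Analysis population the main set is defined by completed pairs ("Primary analyses will be per-protocol (i.e. data where participants completed a pair of experiments"), and for anyone with more than one pair "the data from the experiments where the highest THC dose was administered will be used". The set can therefore mix 20, 40 and 60 mg pairs, with the same THC dose at both visits of a pair.

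Under Pharmacokinetic analyses, geometric means of Cmax and AUC_t are to be reported. For the comparison "of THC and its metabolites across treatment arms" the SAP says "we will use a paired sample t-test or a Wilcoxon rank sum test, depending on the distribution of the data". It does not say whether values are logged before the test is chosen.

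Elsewhere the SAP sets general rules: "We will use linear mixed models to assess the effect of CBD on all continuous outcomes" (Analysis of primary and secondary outcome measures) and "We will therefore include visit number in all models to account for potential order effects" (Order effects). In the Protocol Synopsis, secondary endpoint 9 is "The difference in plasma levels of THC, CBD, and their metabolites".

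**The concern.** The parametric branch respects the pairing and the fallback does not. A rank-sum test compares the CBD and placebo values as if they came from different people. It leaves the between-person spread in the comparison, including any spread caused by different THC doses. When the two visits of a person are positively correlated, its null variance is too large: it rejects too rarely and misses changes that a paired test would find.

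This is the only inferential test the SAP gives for whether CBD alters THC exposure, and that result helps readers interpret any CBD effect or its absence. A non-significant rank-sum result could be read as no pharmacokinetic interaction when the test was simply insensitive. The section also leaves out visit number, which the SAP's general rule puts in all models.

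**Working it through.** **The plan's own figure.** Protocol section 5.1 gives 30 pairs, two-sided alpha 0.05 and 80% power for a paired effect of 0.53. With 29 degrees of freedom and noncentrality 0.53 × √30 = 2.90, paired t-test power is 80.1% and the minimum detectable effect is 0.529. Enrolment is 30 / (1 − 0.25) = 40. Both reproduce. No power is stated for the pharmacokinetic comparison.

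**Assumptions not in the documents.** Log-exposure is bivariate normal with SD 0.5. Within-person correlation ρ is 0, 0.3, 0.5 or 0.7. Where doses are mixed, exposure is proportional to dose, so log(dose/20) is added to both visits of a pair.

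**Why the rank-sum test is conservative here.** It scales the shift by a standard error that assumes independence, while the true one is smaller by about √(1 − ρ). A nominal 5% test therefore rejects under the null only when |Z| > 1.96 / √(1 − ρ). At ρ = 0.3, 0.5 and 0.7 the cut-off is 2.34, 2.77 and 3.58, giving a type I error of about 1.9%, 0.6% and 0.03%. The simulated values below are close to these.

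**Dose mixing adds correlation.** If V is the variance of log(dose/20), the total correlation is (0.25ρ + V) / (0.25 + V). For a 20/40/60 mg mix of 80/15/5%, V = 0.107; for 50/25/25%, V = 0.221. Even at ρ = 0 the total correlation is then 0.107/0.357 = 0.30 and 0.221/0.471 = 0.47.

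**Simulation** (10,000 replicates per setting, 30 pairs, two-sided 0.05, normal-approximation tests with continuity correction). First, the shift is set to the protocol's paired effect: 0.53 × 0.5 × √(2(1 − ρ)) on the log scale.

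| | ρ = 0 | 0.3 | 0.5 | 0.7 |
|---|---|---|---|---|
| Implied exposure ratio | 1.46 | 1.37 | 1.30 | 1.23 |
| Signed-rank power, any dose mix | 77–78% | 77–78% | 77–78% | 77–78% |
| Rank-sum power, single dose | 79% | 67% | 50% | 23% |
| Rank-sum power, 80/15/5% mix | 67% | 50% | 32% | 11% |
| Rank-sum power, 50/25/25% mix | 50% | 32% | 16% | 3% |
| Rank-sum power, equal thirds | 52% | 34% | 17% | 4% |
| Rank-sum type I error, single dose | 4.8% | 2.1% | 0.7% | 0.1% |

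The true ratio shrinks along each row, so the second table holds it fixed.

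| | ρ = 0 | 0.3 | 0.5 | 0.7 |
|---|---|---|---|---|
| Ratio 1.25, single dose: rank-sum | 37% | 35% | 34% | 31% |
| Ratio 1.25, single dose: signed-rank | 36% | 49% | 63% | 84% |
| Ratio 1.5, single dose: rank-sum | 85% | 89% | 92% | 96% |
| Ratio 1.5, single dose: signed-rank | 84% | 94% | 99% | 100% |
| Ratio 1.5, 50/25/25% mix: rank-sum | 60% | 61% | 64% | 68% |

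The dose term cancels in a within-person log ratio, so the signed-rank figures for ratio 1.5 also apply to the mixed-dose row. At a ratio of 2.0, power is at least 98.9% in every setting.

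A second simulation, with spread set by an assumed coefficient of variation (2,500 replicates, single dose, ratio 1.25, ρ = 0.5), gives 38% for rank-sum against 67% for signed-rank at 50%, and 20% against 47% at 70%.

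**How likely the fallback is.** If normality were judged by a Shapiro test at 0.05 on raw within-person differences from such log-normal data, between 26% and 89% of simulated trials would go to the fallback, depending on the setting. On log differences only 4–6% would.

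**The case against.** The strongest reply is that these powers are conditional on a branch that may never be used. Protocol section 5.2 says non-normal data will be transformed before analysis, and the planned geometric means point to a log scale. On that scale the paired t-test would usually apply and nothing is lost. This is fair as far as it goes: the tables show the power of the fallback, not of the whole plan. But the pharmacokinetic section does not say that values are logged, and on raw differences the fallback is a real possibility.

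Second, fixing the paired effect at 0.53 exaggerates the fall in rank-sum power, because the ratio falls from 1.46 to 1.23 as correlation rises. That is correct. At a fixed 1.25-fold change rank-sum power is nearly flat, and the gap opens because the paired test gains.

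Third, SD, correlation, dose mix and dose proportionality are all assumed. The protocol also lets users titrate and lets inhalation be paused, so exposure may not follow nominal dose. The dose-mix rows show direction and possible size; they are not predictions.

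Fourth, a specific section may override a general rule, and a paired t-test is a legitimate simple crossover comparison. The SAP justifies visit number by learning and familiarity with the laboratory, which bear mainly on behavioural outcomes. The missing mixed model is therefore an inconsistency to settle, not an error in itself.

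Finally, this is probably a slip for the signed-rank test, pharmacokinetics are not among the SAP's four hypotheses, and the error is conservative. All true, but an analyst who follows the text literally would run the wrong test, and one who quietly ran the right one would depart from the SAP.

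**Conclusion.** The concern holds. The named fallback does not match the paired design, and nothing in the SAP or protocol corrects it. The loss is nil with one dose and no within-person correlation, and grows with either correlation or dose mixing. For a 1.25-fold change at one dose and a correlation of 0.5, power is 34% instead of 63%. With a single dose the loss matters mainly for ratios below about 1.5. Under a 50/25/25% dose mix it is still large at 1.5 (60–68% against 84–100%). Two-fold changes would be found either way.

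These sizes rest on an assumed log-SD of 0.5 and the other assumptions listed, and apply only if the fallback is used. The consequence is confined to a secondary comparison: the test cannot inflate false positives, the descriptive geometric means would still show a shift, and both primary analyses are unaffected. It should be corrected because the remedy is almost free.

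**What to change.** Minimum: in the SAP's Pharmacokinetic analyses, replace the rank-sum test with the Wilcoxon signed-rank test on within-participant log ratios. State that the paired t-test is also applied to log values, so that both branches use the same scale as the geometric means. This costs one sentence and one line of code.

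Preferred but optional: analyse log Cmax and log AUC_t with the SAP's existing linear mixed model (treatment, visit number, random participant) and report geometric mean ratios with 95% confidence intervals. This removes the test-selection step and settles the inconsistency over visit number, for slightly more code.

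In either case, state whether the 20 mg-only sensitivity analysis also covers the pharmacokinetic comparison. No new data are needed.
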